In the future trial, we will need large, generalizable samples that would be difficult, if not impossible, to recruit at one site. Therefore two sites, Washington University and University of Pittsburgh, will participate in the feasibility RCT. Drs. [name] and [name] will serve as principal investigators (PI). The Steering Committee will include the PIs and Drs [name] and [name] (See *Project Leadership Plan*).

Washington University, Study Coordinating Center: The Study Coordinating Center ([name], Director) will oversee personnel training, protocol implementation, data collection and follow-up. [name] is an orthopedic physical therapist with a Master's of Science in Clinical Investigation. As part of her training (K23HD067343), she successfully completed an exploratory trial to assess the feasibility of MPT in the treatment of PAHD. Washington University provides substantial infrastructure to support this project (See *Facilities and Other Resources*). Our multidisciplinary hip group (See *letters [name], [name], [name], [name]*) has substantial expertise in PAHD and experience in participant recruitment for clinical research. The Data Coordinating Center ([name], director) will administer the study, perform scientific oversight, ensure quality control and perform data analysis.

University of Pittsburgh: The Physical Therapy – Clinical and Translational Research Center (PT-CTRC) ([name], Director) will oversee study implementation at the University of Pittsburgh site. [name] will also guide [name] in developing and implementing methods to optimize treatment fidelity among treatment providers. Methods he has used successfully in his previous RCTs will be used in the proposed study. [name] is an experienced investigator and recognized expert in OA,¹⁶ who has conducted multiple RCTs examining the effectiveness of rehabilitation related to lower extremity disorders.^{1, 17, 45} The PT-CTRC provides significant infrastructure to perform multicenter clinical trials including access to potential participants, facilities, equipment and support for new investigators (See *Facilities and Other Resources*).

[figure not shown]

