Aim 2: Post-treatment improvement in outcomes: In our previous study (K23), we used patient-reported outcomes and 3D motion analysis to assess post-treatment improvement in function and lower extremity movement patterns respectively. We noted, with baseline assessment, that increased hip adduction motion during a single leg squat, may be associated with lower patient-reported function, quantified using the modified Harris Hip Score ($r = -0.28, P = 0.08$) (*unpublished data*). Compared to wait-list control, those who participated in MPT demonstrated improved post-treatment function²¹ (Fig. 2) that was associated with a reduction in hip adduction ($r = -0.60, p=0.001$) (Fig. 3). Additional preliminary data suggests these post-treatment improvements in function are maintained up to 12 months after treatment.²⁰ These preliminary results suggest that MPT may be an effective treatment approach for people with PAHD, however comparison to standard rehabilitation is needed.

Experimental approach

Participant Recruitment: 46 participants will be enrolled. To be enrolled, participants must 1) be 15-40 years old, 2) report deep hip joint or anterior groin pain, confirmed upon physical exam, 3) report pain $\geq 3/10$ and present ≥ 3 months and 4) demonstrate functional limitation with modified Harris Hip Score <90 . Exclusion criteria include 1) previous hip surgery, fracture, pelvic/hip infection, or pain due to high impact trauma, 2) inflammatory disease, e.g. rheumatoid arthritis, gout and 3) neurological involvement affecting balance.

General Procedures

Aim 1: Participant adherence and treatment fidelity: Participant adherence to treatment sessions will be documented by the treatment providers. Participants will complete daily logs of home program performance. To optimize retention, participants will be contacted at regular intervals by the site-specific research coordinator. Any barriers to study participation will be documented and addressed. To optimize treatment fidelity among study personnel, we will use training methods established by [name]. We also will use the treatment fidelity framework developed by the NIH's Behavioral Change Consortium.^{7,8} Treatment providers will be contacted monthly to identify barriers to treatment fidelity. Booster sessions to review key components of study protocol will be provided at months 9 and 15.

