Secondary outcome – Movement pattern: We will use a digital camera to acquire 2D hip motion while participants complete tasks of varying difficulty: step down, single leg squat, drop vertical jump. Markers will be placed on anatomical landmarks of the pelvis and thigh to assist with hip angle measurement. Previously published procedures²⁵ for camera placement and participant positioning will be used to optimize between-site data collection and reduce the effect of projection angles on the 2D measures. Participants will practice each movement prior to testing. We will then collect 3 trials of each movement. Commercially available software will be used to measure peak hip adduction motion. All measurements will be completed by trained personnel at Washington University, who will be blinded to treatment group.

In our **preliminary work**, we used 3D kinematic methods to quantify hip motion during the single leg squat. For the current study, we chose to use a 2D method that can be easily replicated with simple equipment in the clinical setting. To assess our ability to predict 3D peak hip adduction angle using our proposed 2D method, we used digital videos synchronized to the 3D kinematic data collection. Using data from 12 randomly selected participants, we found the correlation between 2D and 3D peak hip adduction to be high ($r = 0.85$, $P < 0.001$). Test-retest reliability of our 2D method is excellent ($ICC_{3,3} = 0.996$); standard error of measurement of 0.47° .

Randomization: Participants will be randomized to 1 of 2 treatment groups in a 1:1 ratio stratified by sex and HOOS Symptoms quartile (as determined from the preliminary data) within each site. Within each stratum, participants will be allocated using a variable block size so that the desired allocation ratio will be maintained at intervals throughout the recruitment process. Randomization sequences will be generated a priori using a formal probability model and will be elicited from the data capture system. Given the nature of the intervention, it is not possible to blind the treatment providers or participants to treatment assignment. Study personnel performing the assessments or the movement pattern measurements will be blinded to group assignment.

Treatment: Treatment for both groups will include 10 supervised sessions over 12 weeks. After randomization,

[figure not shown]

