Post-treatment assessment: Participants will return for questionnaire completion and movement pattern assessment immediately after treatment. We will compare pre-treatment measures to post-treatment measures of both treatment groups to assess change in functional ability (HOOS) and movement patterns. Additionally, participants will complete a questionnaire developed to determine barriers to treatment adherence and to assess 1) treatment receipt, '*did the participant receive the treatment as intended*' and 2) treatment enactment, '*was the participant able to successfully implement their new skills*'.^{7, 8} To assess sustained effects of treatment, participants enrolled at the Washington University site will return for questionnaire completion and laboratory testing 1-2 years after treatment

Additional measures: We will collect additional measures, to assist in the future trial development. To assess the feasibility of using PROMIS, the NIH-funded Patient-Reported Outcomes Measurement Information System for people with PAHD, we will use the computer-adapted version of the physical function and mobility domains. Using previously reported methods,²³ we will assess hip muscle strength pre- and post-treatment. Finally, using additional funding from Washington University (See letter, [name]), participants will complete study questionnaires, electronically administered, 6 and 12 months after treatment to assess durability of post-treatment improvement.

Sample size considerations: With a sample size of 46 (23/group), the 95% confidence bounds (CBs) around our overall rates of adherence and retention will be between 78% and 96%, meaning that estimates will be within 9% of the true rate. The within site and within group estimates of adherence will be within 13% of the true rate. These calculations assume that the observed rates will be at least 90%, which is reasonable to expect based on our preliminary data. Aim 2 will estimate intervention effect sizes and as such, the study is not designed to generate definitive results. However, with at least 20 participants/group completing pre- and post-testing, the study will have 80% power to detect large effect sizes of 0.9 or above, with 95% CBs between 0.27 and 1.53. We note that preliminary data for the primary outcomes indicate that approximately 50% of the variance in change is explained by the pre-treatment value, and thus power and precision will be increased by including this covariate in the analyses.

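### Do 16 randomisation strata for 46 participants leave the 1:1 allocation unprotected?

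*Combined protocol and SAP*

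**What the plan says.** The overview of the approach states that "two sites, Washington University and University of Pittsburgh, will participate in the feasibility RCT", and Participant Recruitment states that "46 participants will be enrolled". Under Randomization, the two arms are allocated equally, and the allocation is "stratified by sex and HOOS Symptoms quartile (as determined from the preliminary data) within each site". Blocking operates inside each of these cells: "participants will be allocated using a variable block size so that the desired allocation ratio will be maintained at intervals throughout the recruitment process". The section gives no block sizes, no cap on imbalance across strata and no minimisation.

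Sample size considerations starts from 23 per group. It bases its power statement on a design "with at least 20 participants/group completing pre- and post-testing", and it gives precision for adherence overall, within site and within group. Statistical Analysis specifies an ANCOVA of change with the pre-treatment value as covariate, and unadjusted Wilcoxon comparisons of adherence, retention and fidelity rates between sites and between groups.

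**The concern.** A permuted block restores equality only when it is completed. With 16 separate sequences and 46 people, many sequences will stop part-way through a block, and the leftovers add up across strata. On this reading the plan claims a balance that its scheme cannot deliver.

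The stakes would be the 23 per group and 20 completers per group in the sample size section, and the arm balance inside each site. The quartile factor also looks like poor value, because the ANCOVA already adjusts for the pre-treatment score. Four site-by-sex strata would hold the arm counts much closer at no cost in participants.

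**Working it through.** **Inputs from the plan.** N = 46, 1:1 allocation, 2 sites, 2 sexes, 4 quartiles, effect size 0.9, 20 completers per group, expected rates of at least 90%.

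**Assumptions.** Two-sided 5% test. Block sizes drawn at random from {2,4} or {4,6}. Unless stated otherwise, equal sites, 70% female and equally filled quartiles. Simulated figures rest on 3,000 or more trials per scheme.

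**The plan's own figures.**
- Power for a two-sample t test uses noncentrality d x sqrt(n1 n2/(n1+n2)). For 20/20 this is 0.9 x sqrt(10) = 2.85 on 38 degrees of freedom, giving 79.2%. The plan says 80%.
- The Wilson interval for 90% of 46 is 78.0% to 95.8%. The plan says 78% to 96%.

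Both reproduce.

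**Strata.** 2 x 2 x 4 = 16, and 46/16 = 2.9 per stratum. The number that never complete a block depends on the unstated sizes. With equally likely strata it is 7.1 of 16 (44%) for {2,4} and 12.9 of 16 (80%) for {4,6}. So it is not true for every plausible choice that most strata never fill a block. It does hold for both sets that most strata end inside an open block (10.5 and 12.9 of 16, at 70% female).

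**Arm counts.**

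| Scheme | P(20:26 or worse) |
|---|---|
| 16 strata, blocks 2/4 | 14% |
| 16 strata, blocks 4/6 | 21% |
| 4 strata (site x sex) | 0.2% to 1.2% |
| Simple randomisation | 46% |

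**What a 20:26 split costs.** The variance ratio against 23:23 is (1/20 + 1/26)/(2/23) = 1.017. Power at 0.9 is 84.7% for 23/23 and 84.1% for 20/26, a loss of 0.6 points in a trial already that unbalanced. Averaged over simulated trials with 90% retention, power is 80.2% to 80.3% with 16 strata and 80.3% to 80.4% with four.

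**What the quartile factor buys.** With 16 strata the standard deviation of the between-arm difference in mean baseline HOOS Symptoms is 0.18 to 0.20 baseline SDs. With four strata it is 0.29. The ANCOVA variance factor relative to perfect balance, which counts both unequal arms and baseline imbalance, is 1.014 to 1.019 with 16 strata and 1.025 with four. The simpler scheme would thus raise the variance by 1.025/1.019 - 1 = 0.6% to 1.025/1.014 - 1 = 1.1%.

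**Adherence precision.** The plan quotes 13% within site and within group. The Wilson half-width for 90% of 23 is 12.7%, so each is a separate rate on about 23 people. A within-site rate pools both arms, so arm imbalance inside a site cannot affect it. For a within-group rate, an arm of 20 widens the half-width from 12.7% to 13.7%.

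**The case for a change.** The strongest opposing point is the completer target. With 90% retention, both arms reach 20 completers in 41% to 47% of trials with 16 strata and 57% to 61% with four. That gap is real. But exactly 23/23 reaches the target only 65% of the time (P(Bin(23, 0.9) >= 20) squared), so attrition accounts for much of the shortfall. The 20 per group is an input to the power statement, and power hardly depends on how the completers divide: 79.2% at 20/20, 80.4% at 18/24 and 79.1% at 17/24.

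The second point is balance within sites. A difference of 4 or more in at least one site arises in 27% to 41% of trials, against 0.5% to 2.4% with four strata. At any given site it is 14% to 22%. The ANCOVA does not name site, so the analysis does not repair this. The looseness stands, but no site-by-arm estimate is planned.

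The third point is that stratifying on a score already in the model is redundant. That is only partly so. Each outcome is adjusted for its own pre-treatment value, so HOOS Symptoms is not a covariate for movement pattern, and the between-group Wilcoxon comparisons are unadjusted. Four longer sequences with blocks of 2 and 4 would also make assignments easier to guess in a trial whose providers and participants are unblinded.

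Minimisation with a random element on site, sex and HOOS Symptoms would keep both kinds of balance. It would cut the variance by under 1% and replace sequences generated in advance with dynamic allocation. It is a reasonable option, not a correction.

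**Conclusion.** The count of 16 strata is right, and arm totals may well differ by several. The stronger reading, that the ratio is unprotected, fails. A serious split is less than half as likely as under simple randomisation (14% to 21% against 46%). The plan promises the ratio only at intervals within strata, which describes how blocks work and does not guarantee 23/23. Leaving block sizes out of a protocol is ordinary practice to protect concealment.

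Fewer strata would gain about 0.2 power points at most and give up some prognostic balance, in a study that says it is not designed to give definitive results. This is a fair trade-off with nothing material to gain from changing it.

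The conclusion rests on assumed block sizes and on the assumed site, sex and quartile distributions. The quartile cut-points come from the earlier study, which randomised 35 people, so strata may fill less evenly than assumed. With equally likely strata and block sets from {2,4} up to {4,6,8}, the chance of 20:26 or worse ranges from 14% to 27%, still well under 46%. Even 18/28 leaves power at 83.0% against 84.7% for 23/23.

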We anticipate no problems enrolling sufficient participants for this feasibility study. We were able to enroll 3-5 participants per month during our previous study. To improve our likelihood of meeting recruitment goals, we have added the University of Pittsburgh site and established collaborations with additional healthcare providers in St. Louis. We have also removed the restriction from the previous study for body mass index (previously <30 kg/m² required for kinematic testing). Support from the Data Coordination Center ([name], Director) will assist in optimizing retention rate and patient follow-up. Additionally, we will provide compensation of \$25/hour to offset travel effort and costs related to the testing sessions and treatment will be provided at no charge.

Statistical Analysis: The primary data analyses for Aim 1 will be descriptive, and include reporting the rate of recruitment, screening, and enrollment for all potential participants considered for the study; and reasons for non-enrollment. Adherence, retention, and fidelity rates will be categorized using the specified thresholds and reported with 95% CBs. Uncategorized rates will be compared between sites and groups by Wilcoxon's test. Aim 2 will generate estimates of effect sizes. We will report change between pre-and post-treatment with 95% CBs. Inferential analyses will compare the change in response to treatment using analysis of covariance (ANCOVA) where change is the dependent variable and the pre-treatment value is the covariate. Accounting for variation in pre-treatment function will increase the precision of the between-group comparisons and also adjust the treatment effect estimates for possible imbalances between groups. If statistical assumptions are not satisfied, transformations will be explored or nonparametric covariance analyses³⁵ will be used.

Data Management and Quality Control: Study data will be electronically captured using the REDCap system hosted in a limited access data center managed by the Data Coordinating Center. Additional quality control programs will verify that study identification numbers are accurately labeled, evaluate consistency over time, and check for incomplete or overdue data. Routine reporting will monitor recruitment and retention, overall quality, and protocol deviations. Throughout the study, standardization of procedures across sites will be ensured by dynamic training and monitoring that includes site visits and remote auditing.

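### The 13-week HOOS, the self-reported primary outcome, is collected only at a return visit, and no remote route is described for people who do not attend

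*Combined protocol and SAP*

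**What the plan says.** The protocol names the HOOS, a patient-reported questionnaire, as the primary outcome (Primary outcome – Function). That section places it at the pre- and post-treatment testing sessions. General Procedures, Aim 2, has participants come back for testing 13 weeks after enrolment. Post-treatment assessment says the same: "Participants will return for questionnaire completion and movement pattern assessment immediately after treatment".

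A different procedure is written for later follow-up. Under Additional measures, "participants will complete study questionnaires, electronically administered, 6 and 12 months after treatment". All questionnaire responses are held in REDCap at every time point (Primary outcome – Function).

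Sample size considerations makes its power statement conditional on a completer count: "with at least 20 participants/group completing pre- and post-testing", in which case "the study will have 80% power to detect large effect sizes of 0.9 or above, with 95% CBs between 0.27 and 1.53". The rate calculations in the same section rest on a floor: "These calculations assume that the observed rates will be at least 90" per cent.

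Statistical Analysis specifies ANCOVA with change as the dependent variable and the pre-treatment value as covariate. It gives no method for a missing post-treatment HOOS.

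**The concern.** Among the 13-week measures, the movement and strength tests need the participant in the room; a questionnaire does not. Tying the HOOS to the visit means that a missed visit costs the primary outcome as well as the physical tests. A participant could then supply a HOOS at 6 months and have none at 13 weeks.

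Two things are at stake. The first is bias. Someone without a 13-week HOOS has no change score and so drops out of the ANCOVA. Participants and therapists know the assignment, so attendance could plausibly depend on arm and on how the hip is doing. The second is the feasibility readout. Retention is an Aim 1 result meant to inform the larger trial. If visit attendance and primary-outcome completion are the same event, the trial cannot show which of them would limit its successor.

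**Working it through.** **Inputs.** 46 participants, 23 per group, and at least 20 completers per group for the power statement (Sample size considerations); 1:1 allocation (Randomization); retention of at least 90% (Sample size considerations). In the preliminary study, 2 of 18 treated and 1 of 17 wait-list participants were lost, so 16/18, 16/17 and 32/35 = 91.4% were retained (Preliminary studies, Aim 1). Alpha is not stated for the power figure; two-sided 0.05 is assumed, in line with the 95% bounds used throughout. Arms are taken as independent.

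**The plan's own figures reproduce.**
- Power with 20 per group at effect size 0.9: 81.2% by the normal approximation and 79.2% by the noncentral t, against 80% stated.
- Effect-size bounds: 0.9 ± 1.96 × √(2/20) = 0.28 to 1.52 (0.26 to 1.54 with the t quantile), against 0.27 to 1.53 stated.
- Wilson bounds for 90% of 46: 78.0% to 95.8%, against 78% to 96% stated.

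**Expected loss at 90%.** 46 × 0.10 = 4.6 participants without a 13-week HOOS.

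**Chance that both groups reach 20.** With X ~ Bin(23, p), the probability is P(X ≥ 20) for one arm, multiplied across the two arms. At p = 0.90:

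P(X ≥ 20) = 0.2153 + 0.2768 + 0.2265 + 0.0886 = 0.807, and 0.807² = 0.652.

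| Retention | One arm | Both arms |
|---|---|---|
| 90% (plan's floor) | 80.7% | 65.2% |
| 16/18 and 16/17, by arm | 75.2% and 95.7% | 71.9% |
| 32/35 = 91.4% | 87.1% | 75.8% |
| 95% | 97.4% | 94.9% |

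**What falling short costs.** t-test power at effect size 0.9 is 79.2% with 20 per group, 77.0% with 19 and 74.6% with 18. At 90% retention both groups reach at least 18 with probability 95.5%, and power averaged over the completer counts is 80.4%. If the baseline value explains 50% of the variance in change, as the protocol reports from preliminary data, the effect size becomes 0.9/√0.5 = 1.27 and power is about 96% even with 18 per group.

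**What a remote route could recover.** The documents give no response rate for non-attenders, so a range is needed. If a share f of them answers, the completion rate is 0.90 + 0.10f:

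| f (assumed) | HOOS completion | Both groups ≥ 20 |
|---|---|---|
| 0% | 90% | 65% |
| 25% | 92.5% | 83% |
| 50% | 95% | 95% |

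**Scale of possible bias (illustration).** With 10% missing in each arm, a completers-only mean differs from the full-arm mean by 0.10 × (completers' mean − non-completers' mean). The unadjusted arm difference is therefore biased by 0.10 × (that gap in one arm − that gap in the other). If the gaps differ by 6 or 9 points (the minimum important changes the protocol cites for ADL and Symptoms, used here only as yardsticks), the shift is 0.6 or 0.9 points. If the gaps are equal, it is zero.

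**The case against.** The strongest reply is that the documents never forbid remote completion. The questionnaire is already in REDCap. Coordinators contact participants regularly, tailored survey methods are used to encourage response, overdue data are checked, testing sessions are compensated, and a Manual of Procedures not included here may cover the case. This partly stands: loss of the outcome is inferred from what the text omits. But the protocol writes attendance for 13 weeks and electronic administration for 6 and 12 months, and a site following it would treat these as different procedures. None of the retention measures says what happens to the HOOS when someone does not come.

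A reader might infer that the visit requirement is why 20 per group is reached only about 65% of the time, or that the trial is therefore underpowered. The documents support neither. The 65% comes from 23 per group and a 90% rate, whatever the mode of collection, and 90% is the plan's floor. Missing the count by one or two per group costs about 2 to 5 points of power before the covariate gain, and the protocol says Aim 2 is not designed to be definitive.

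The preliminary study does not show the feared pattern either. Its three losses did not return after baseline testing. The two in the treated arm left before treatment began, and the 16 who were treated attended nearly every session. Nothing shows that those who left would have answered remotely.

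Two further points stand. The completer condition covers all pre- and post-testing, so a remote HOOS would not restore the movement outcome. And completing the form in the same setting before and after keeps the mode constant, which is a legitimate aim.

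**Conclusion.** The point holds as a cheap improvement to a stated procedure. As written, a participant who misses the 13-week visit has no primary outcome and is left out of the ANCOVA, although the trial already has the means to ask for it. The case rests on avoidable missing primary data in an unblinded comparison and on a clearer feasibility result; it does not rest on lost power.

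In size, about 4.6 of 46 would be missing at the 90% floor. The probability that both groups reach 20 is about 65% there and 72% to 76% at the preliminary rates, assuming independent arms. The gain from a remote route is unknown and could be nil: it depends wholly on how many non-attenders would reply, for which the documents give no figure. A reader might take 95% as the expected result of the change, but that needs half of the non-attenders to respond.

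**What to change.** Add to Post-treatment assessment that the 13-week HOOS is sent electronically through REDCap to every randomised participant who does not complete it at the visit, whether or not they attended or finished treatment. Record the mode of completion. For Aim 1, report visit retention and primary-outcome completion as two separate rates.

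The cost is a few sentences and the use of a system already in place. The downside is a small number of responses in a different mode, concentrated among non-attenders, so mode and non-attendance cannot be separated; recording the mode at least makes this visible. The movement and strength outcomes would still be missing for these participants.

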Significance and future directions: Information from the current study regarding the participants' ability to adhere to treatment, the treatment providers' ability to adhere to the treatment protocol and effect size estimates will guide the future, large RCT. Should the feasibility study indicate that modifications are needed, these will be made prior to the large RCT. Feedback from study participants and the treatment providers will be used to improve participants adherence and treatment fidelity. The future RCT will include assessment of patient-reported function and movement patterns from the proposed study and bony abnormalities. A better understanding of the association among these factors and treatment prognosis will help us develop improved treatment strategies and to better match treatment to patients.

Intra-articular, prearthritic hip disorders result in significant limitations in the young adult and are likely precursors to osteoarthritis. MPT is an innovative treatment approach with the potential to optimize treatment outcomes, nonsurgical and surgical, for people with PAHD. Further, MPT may provide a strategy for injury prevention, particularly those injuries of insidious nature. Ultimately this work will lead to better overall outcomes, reduced healthcare cost and reduced patient burden.

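### The 9% and 13% precision claimed for Aim 1 are interval half-widths; from an observed 90%, the lower 95% bound is 12 points away at n=46 and about 18 at n=23

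*Combined protocol and SAP*

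**What the plan says.** Under Sample size considerations (section C, Approach), the protocol gives the basis for Aim 1 precision. For 46 participants, 23 in each arm, it says of the 95% bounds on the overall rates that they "will be between 78% and 96%, meaning that estimates will be within 9% of the true rate". The next sentence extends this to subsets: "The within site and within group estimates of adherence will be within 13% of the true rate". The condition follows: "These calculations assume that the observed rates will be at least 90" percent. No interval method is named, and no bounds are printed for the smaller subsets.

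Under Statistical Analysis, the Aim 1 rates are to be presented in the same form: "Adherence, retention, and fidelity rates will be categorized using the specified thresholds and reported with 95% CBs". No interval method is named there either.

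**The concern.** The paragraph takes an observed rate of 90%, prints a lower bound of 78%, and then says the two are at most 9 points apart. A true rate of 78% lies inside the printed bounds and is 12 points from the estimate, so the inference fails on the plan's own numbers.

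The side that is understated is the one that matters. Adherence, retention and fidelity are to inform the larger trial, and Significance and future directions says: "Should the feasibility study indicate that modifications are needed, these will be made prior to the large RCT". A planner will want to know how far below the observed rate the truth could plausibly lie. For the overall rates, the printed 78% lets a careful reader correct the 9. For the rates within a site or group, only the 13 is given.

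**Working it through.** **Inputs**

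- n = 46 overall and 23 per group (Sample size considerations), with 1:1 allocation (Randomization).
- Observed rate p = 0.90, the lowest value the plan assumes.
- 95% confidence, taken as two-sided because a lower and an upper bound are given; z = 1.96.
- 23 per site is an assumption. The text gives 23 only for the groups, and the flow diagram is not reproduced in the copy reviewed.

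**Step 1: reproduce the plan's figures.** The Wilson score interval is

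centre = (p + z²/2n) / (1 + z²/n)

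half-width = z·√[p(1−p)/n + z²/4n²] / (1 + z²/n)

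- n = 46: centre = 0.9418/1.0835 = 0.869; half-width = 0.0962/1.0835 = 0.089; interval 78.0% to 95.8%.
- n = 23: centre = 0.9835/1.1670 = 0.843; half-width = 0.1483/1.1670 = 0.127; interval 71.6% to 97.0%.

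Rounded, these give 78, 96, 9 and 13, which are all four printed figures. Of the eight standard methods tried, only Wilson reproduces all four. For example, the simple normal (Wald) interval gives 81.3% to 98.7% at n=46. Agresti-Coull rounds to 78 and 96 at n=46 but has a half-width of 13.8 at n=23.

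**Step 2: measure from the estimate instead of the midpoint.**

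| n | Observed | Lower bound | Upper bound | Distance below | Distance above | Plan states |
|---|---|---|---|---|---|---|
| 46 | 90% | 78.0% | 95.8% | 12.0 | 5.8 | 9 |
| 23 | 90% | 71.6% | 97.0% | 18.4 | 7.0 | 13 |

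Understatement of the lower distance: 1 − 9/12 = 25% at n=46, and 1 − 13/18.4 = 29% at n=23.

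**Step 3: test the words 'at least'.** Higher observed rates might bring the lower bound inside the stated margin, so each attainable count at or above 90% was checked.

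| Count | Lower bound | Distance below estimate |
|---|---|---|
| 42/46 | 79.7% | 11.6 |
| 43/46 | 82.5% | 11.0 |
| 44/46 | 85.5% | 10.2 |
| 45/46 | 88.7% | 9.2 |
| 46/46 | 92.3% | 7.7 |
| 21/23 | 73.2% | 18.1 |
| 22/23 | 79.0% | 16.6 |
| 23/23 | 85.7% | 14.3 |

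At n=46 the margin of 9 is met only at 46/46, although 45/46 rounds to 9. At n=23 the margin of 13 is never met.

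**Step 4: read the sentence as a sampling statement.** For a fixed true rate, this is the exact binomial probability that the estimate falls within the stated margin.

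- n = 46, within 9 points: 0.89 at a true 78%, 0.86 at 80%, 0.88 at 82%, 0.94 at 85%, 0.96 at 87%, 0.96 at 90%.
- n = 23, within 13 points: 0.84 at a true 72%, 0.85 at 75%, 0.89 at 80%, 0.93 at 85%, 0.98 at 90%.

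The claim holds at a true 90% but not over the lower part of the range that the intervals allow.

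**Step 5: sensitivity.** With the other asymmetric methods, the distance below an observed 90% runs from 11.1 (Jeffreys) to 13.3 (continuity-corrected Wilson) at n=46, and from 16.9 to 21.1 at n=23. If the sites enrolled, say, 30 and 16 (illustrative numbers only), the Wilson bounds at 90% would be 74% to 97% (16 points below) and 67% to 98% (23 points below).

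**The case against.** The best defence is that nothing was miscalculated. Every printed number reproduces, and a half-width was merely described in words that suit a symmetric interval. Read as a planning statement about sampling error, the sentence is true at a true rate of 90%: the probabilities are 95.6% for 9 points at n=46 and 97.7% for 13 points at n=23. It also holds at the higher true rates checked.

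That reading is fair as far as it goes, but it is not what the paragraph says. The paragraph conditions on the observed rate and presents the 9 as what the 78% to 96% bounds mean. Those bounds admit true rates at which the statement fails.

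Other parts of the defence stand:

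- This is an error of interpretation, not of computation.
- The n=23 result depends on carrying over the method that fits n=46, and 90% of 23 is 20.7 people, which cannot be observed. The attainable distances are 14.3 to 18.1, still all above 13.
- Site sizes may appear in the missing flow diagram, so their absence is not held against the plan.
- The final report will show actual confidence bounds, so later planners need not rely on the 9 and 13.

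**Conclusion.** The concern holds, as a minor point. At an observed 90% the lower 95% bound lies 12 points below the estimate overall, against a stated 9. Within a group of 23 it lies about 18 points below, against a stated 13. The first figure needs only the plan's own numbers. The second assumes the Wilson method (17 to 21 with other asymmetric methods) and, for sites, 23 participants each.

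The printed bounds of 78% to 96% are correct. Aim 1 is descriptive, and nothing in the text shows that 46 participants were chosen to meet the 9%. Even so, this is the only precision argument offered for Aim 1, and it makes the downside look smaller than it is.

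**What to change.** In Sample size considerations, name the interval method (Wilson) and replace the two margin statements with text such as: 'At an observed rate of 90%, the 95% confidence bounds (Wilson) are 78% to 96% overall, with the lower bound 12 points below the estimate. They are about 72% to 97% within a group of 23, or a site enrolling 23, with the lower bound 18 points below.' Describing these as confidence bounds avoids suggesting a hard limit on the true rate. If planned site numbers differ from 23, print the bounds for each site.

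Name the same method in Statistical Analysis, so that it is settled how the reported bounds will be calculated.

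The cost is wording only. Sample size and analysis stay as they are, and the stated precision becomes less favourable.
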